6.8 CRITERIA FOR STOPPING NUCLEOSIDE ANALOGUE

Participants who complete the treatment period will stop NUC *therapy* if laboratory results on samples taken at end-of-treatment or at any of the follow-up visits show:

- ALT<1.25× baseline values, AND
- HBV DNA<LLOQ or<20 IU/mL, AND
- negative HBeAg, AND
- HBsAg <100 IU/mL and $\geq 1 \log_{10} IU/mL$ decline from baseline or HBsAg loss.

These criteria for stopping NUCs do not apply to any patients who have discontinued study drug prematurely for any reason.

7. DISCONTINUATION OF STUDY TREATMENT, PARTICIPANT DISCONTINUATION/WITHDRAWAL FROM THE STUDY AND LOST TO FOLLOW-UP

Participants have the right to voluntarily discontinue study treatment or withdraw from the study at any time for any reason.

An excessive rate of withdrawals (either participants discontinuing study treatment or withdrawing from the study) can render the study non-interpretable. Therefore, unnecessary withdrawal of participants should be avoided and efforts should be taken to motivate participants to comply with all the study-specific procedures as outlined in this protocol.

Details on study and site closures are provided in Appendix 1.

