8.3.8 Management of Specific Adverse Events

8.3.8.1 Management of Virological Breakthrough

Participants with suspected virological breakthrough (HBV DNA > 100 IU/mL or > 1-log increase from nadir) during treatment will attend a study visit (scheduled or unscheduled) within 2 weeks for:

- a confirmatory test of HBV DNA and plasma drug levels
- thorough evaluation of adherence and factors that may be affecting treatment compliance

If virological breakthrough is confirmed:

- the sample will be further tested for HBV genome characterization through HBV DNA sequencing and where feasible phenotyping
- NMEs will be discontinued
- The investigator will manage the CHB participant's NUC treatment, according to current guidelines and local regulations (guided by participant's treatment history, assessment of adherence, HBV DNA levels, and any available result of drug resistance testing).

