8.3.8.2 Management of Virological Relapse

Participants who have discontinued all study treatments (NME combinations) including NUC therapy should be followed up every 2 weeks for first 12 weeks, thereafter monthly up to week 48 of the follow up period to enable early detection of HBV DNA rebound and appropriate management of virological relapse.

In addition, participants with HBV DNA > 20 IU/mL but < 2,000 IU/mL in follow-up, should undergo monitoring every two weeks.

Participants who discontinue all study treatment (NME combination and NUC therapy for the treatment arms or NUC therapy for the NUC control arm) and subsequently experience virological relapse (HBV DNA > 2,000 IU/mL) during the follow-up period will undergo weekly monitoring: an unscheduled blood sample will be collected for potential HBV genome characterization and where feasible phenotyping.

NUC therapy *should* be restarted in the following scenarios:

- *HBV DNA* > 20,000 *IU/mL* (regardless of other biochemical parameters or ALT values)
- HBV DNA > 2,000 IU/mL and ALT > 1.5 x ULN
- HBV DNA > 2,000 IU/mL and ALT ≤ 1.5 x ULN and if the retest (central or local laboratory) of HBV DNA performed within 1 week after availability of the initial results from the central laboratory confirms HBV DNA > 2,000 IU/mL (regardless of ALT values or other biochemical parameters)
- Immediately restart treatment in participants with clinically significant signs of decreasing liver function based on laboratory findings (e.g., INR, direct bilirubin) or clinical assessments (e.g., ascites, hepatic encephalopathy) regardless of HBV DNA or ALT levels.

For these additional unscheduled monitoring visits, the following laboratory assessments should be performed using the unscheduled lab kit: hematology, chemistry, coagulation, GLDH, urinalysis, HBV serology, HBV DNA quantitative, Total HBsAg, HBcrAg, and HBV RNA quantitative.

Note: The guidance for the management of virological relapse (frequency of monitoring, laboratory assessments, NUC restarting rules) described in this section should be followed in conjunction with the guidance for the management of elevated ALT levels described in Section 8.3.8.3.

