8.7 PHARMACODYNAMICS AND BIOMARKERS ASSESSMENTS

Pharmacodynamic and biomarker analyses that are specific to a treatment arm are stated in each respective appendix. Pharmacodynamic and biomarker analyses that are applicable to all treatment arms are described below.

8.7.1 HBV Dynamic Biomarker Assessments

The following well-established HBV laboratory tests will be measured using serum samples: quantitative and qualitative HBsAg, quantitative anti-HBs, qualitative HBeAg, semi-quantitative HBeAg (calculated), and qualitative anti-HBe.

Additional HBV dynamic biomarkers may be measured in all or some participants, as appropriate. This may include, but not be limited to, quantitative HBV RNA, quantitative HBcrAg, quantitative total anti-HBc, and quantitative total HBsAg (post-dissociation of HBsAg/HBsAb complexes/components of HBsAg) using plasma or serum samples.

8.7.2 HBV DNA Monitoring

The emergence of a virological breakthrough while on NUC therapy, or the emergence of a virological relapse in participants taken off NME combination and NUC therapy during the follow-up period, will be monitored through the quantification of HBV DNA in plasma. In the event that the HBV DNA level is above the defined thresholds for potential virological breakthrough (HBV DNA > 100 IU/mL or 1-log above nadir during treatment) or relapse (> 2,000 IU/mL for participants off NUC therapy) (as defined in Section 8.3.8), a plasma sample will be collected for a confirmatory quantification of HBV DNA at an unscheduled visit or at the next visit of the participant.

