4.5 SAFETY ANALYSES

All safety analyses will be based on the safety analysis population grouped according to the treatment assigned at randomization.

The safety data, including AEs, reasons for withdrawal from treatment and study, laboratory data, ECGs, concomitant medications, vital signs, and physical examination results will be listed and summarized descriptively. Marked abnormalities will be flagged for laboratory data. As appropriate, listings, summary tables and graphs (participant plot and/or mean plots) will be provided for safety and tolerability assessments.

Key Definitions:

Modified Injection Site Reaction: A modified ISR will be defined as, an ISR for which the criteria for a 4-hour post dose injection site reaction is met.

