For Statistical Programming team, please refer the document (Safety Analysis Impact of COVID-19 (All Domains) v0.1) guidance for additional TLGs in case moderate to major impact on the study.

Virological Breakthrough/ Relapse:

The number of participants who had virological breakthrough and relapse will be presented by treatment arm as collected on the CRF, a listing will be provided..

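### Virological relapse is tabulated only as a CRF count per randomized arm, so the plan gives no relapse risk among the participants who stopped NUC, who are the only ones who can relapse

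*SAP*

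**What the plan says.** SAP 4.5.3 (Virological Breakthrough/Relapse) states: "The number of participants who had virological breakthrough and relapse will be presented by treatment arm as collected on the CRF", and adds a listing. It names no denominator. Two general rules fill the gap. SAP 4 presents categorical variables as counts with percentages, and SAP 4.5 fixes the population: "All safety analyses will be based on the safety analysis population grouped according to the treatment assigned at randomization".

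The protocol gives the two events different risk sets.

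- **Relapse.** Protocol 8.7.2 sets the threshold as "relapse (> 2,000 IU/mL for participants off NUC therapy". Protocol 8.3.8.2 places it after withdrawal of everything: "Participants who discontinue all study treatment (NME combination and NUC therapy for the treatment arms or NUC therapy for the NUC control arm) and subsequently" cross the threshold in follow-up.
- **Entry to the relapse risk set.** Protocol 6.8 opens: "Participants who complete the treatment period will stop NUC" if ALT, HBV DNA, HBeAg and HBsAg conditions are all met. The HBsAg condition is a level below 100 IU/mL together with at least a 1 log10 "decline from baseline or HBsAg loss". Participants who stopped study drug early are excluded from this rule.
- **Breakthrough.** Protocol 8.3.8.1 defines it on treatment: "Participants with suspected virological breakthrough (HBV DNA > 100 IU/mL or > 1-log increase from nadir) during treatment".

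**The concern.** The relapse risk set is a subgroup selected by response after randomization, and the planned table ignores it. A count per arm mixes how many people stopped NUC with how often a person who stops then relapses. The second quantity is the one that the intensified off-NUC monitoring and the NUC restart criteria in Protocol 8.3.8.2 are concerned with.

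The counts also lack a common base. The control arm keeps growing as arms are added (Protocol Figure 1 footnote, SAP Appendix 1), and other arms may receive additional participants (Protocol 9.2).

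A second weakness is the source. Relapse is a numeric threshold on a scheduled quantitative test. Protocol 8.3.8.2 states the threshold alone, while 8.7.2 calls for a confirmatory sample. Sites could therefore record either first or confirmed values, and the SAP does not say which counts.

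**Working it through.** **Plan's own figure.** The documents give no figure for relapse, breakthrough or NUC stopping. The only related numbers are the sample-size inputs in SAP 2.2: 3% control response, a 30-point difference (so 33% active), 30 per arm, two-sided 5%, continuity-corrected chi-squared, 78% power. Inverting the correction gives n_eff = 30 − 2/0.30 + 1/(30 × 0.30²) = 23.70, and power at that size is 78.6%. The stated figure reproduces. It does not bear on relapse, but it supplies the response rates used below.

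**Inputs for the illustration**

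- N = 30 per arm (SAP 2.2).
- q, the share of the arm that stops NUC: not in the documents. Assumed 3% for control and 20% to 60% for active arms. The 3% and 33% borrow the planning response rates. The 60% borrows the Phase 1 share with HBsAg below 100 IU/mL (Protocol A9.2), which is a high-end proxy because it meets only one part of the stopping rule.
- r, the relapse risk among stoppers: not in the documents. Assumed 10% to 50%.

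**Formulas.** At risk = N × q. Expected relapses = N × q × r. Arm-level percentage = q × r. Ratio of the risk among stoppers to the arm-level percentage = r/(q × r) = 1/q.

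**Results at r = 30% in every arm**

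| q | At risk (of 30) | Expected relapses | % of arm | % of stoppers | 1/q |
|---|---|---|---|---|---|
| 3% | 0.9 | 0.27 | 0.9 | 30 | 33 |
| 20% | 6.0 | 1.80 | 6.0 | 30 | 5.0 |
| 33% | 9.9 | 2.97 | 9.9 | 30 | 3.0 |
| 60% | 18.0 | 5.40 | 18.0 | 30 | 1.7 |

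The same risk per stopper gives arm percentages from 0.9 to 18.

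**How often would the active count exceed control at equal r?** Take A ~ Bin(30, q·r) and C ~ Bin(30, 0.03·r), independent, and sum Pr(A = i) × Pr(C < i) over i.

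- q = 33%: 60% at r = 10% (with a 37% chance of a tie), 91% at r = 30%, 98% at r = 50%.
- q = 60%: 82%, 99% and above 99.9%.

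Expected counts are equal only if the active risk per stopper is 0.03/q of the control risk: 0.09 at q = 33% and 0.05 at q = 60%.

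**Control.** The chance of no stopper at all is 0.97^30 = 40%.

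**Do other planned outputs supply the missing rate?**

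- SAP 4.3 gives HBV DNA below LLOQ, 200 and 2,000 IU/mL at 12-week points by arm, not split by NUC status. Because a relapse prompts weekly checks and possible NUC restart, it can arise and resolve between those points.
- SAP 4.4 has a relapse rate, but it is HBsAg rebound after HBsAg loss, a different event.
- SAP 4.6.1 lists those who met the stopping criteria and stayed on NUC. No table of those who stopped is planned.
- SAP 4.5.3.1 provides individual ALT/virology profiles, which can be read case by case only.

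None gives relapse per person who stopped NUC.

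**The case against.** The strongest reply is that the SAP promises a count and a listing, and calls neither a risk after NUC withdrawal. Counted over the randomized arm, relapse is a valid description of the burden of a regimen together with its NUC-stopping rule. The rate among stoppers answers a different question in a response-selected subgroup, so it is not a fair comparison between arms either. All of this stands, and it is why the arm-level figure should be kept and no test added.

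It can also be said that the package allows reconstruction. NUC exposure is listed (SAP 4.5.1), HBV treatment is flagged among concomitant medications (SAP 4.5.3), unscheduled laboratory values enter the profile plots (SAP 4.5.3.1), and table layouts are deferred to an output specification that is not available here. That is partly right, but reconstruction by hand from listings is not a planned analysis.

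On the source, the CRF is not simply inferior. Relapse and breakthrough are reportable as adverse events (Protocol Appendix 3, Section 9). A relapse retest may be done locally (Protocol 8.3.8.2), and local results used for decisions are entered as eCRF comments (Protocol Appendix 4). A flag built only from central laboratory data could miss events.

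Three stronger readings are tempting, and the documents do not support them.

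- A reader might infer that breakthrough has the same defect. It is an on-treatment event, so the dosed arm is already about the right denominator.
- A reader might infer that the plan understates relapse risk. That holds only if the count is divided by the arm size and then read as a risk among stoppers.
- A reader might infer that effective arms will look worse than control. That depends on q and r, which the documents do not give. An arm with durable responses could show few relapses, and no ranking or test is planned.

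**Conclusion.** The point holds for virological relapse. The planned table cannot give the risk of relapse after stopping NUC, and no other planned output does. That the number at risk will differ between arms is an expectation drawn from the response-dependent stopping rule in Protocol 6.8; the documents give no stopping shares. Under the assumed shares, an arm-level percentage falls short of the risk among stoppers by a factor of about 1.7 to 5 in active arms (q from 60% to 20%) and about 33 in a control arm with 3% stopping. At an equal 30% risk per stopper, the expected counts are 0.27 for control and 2.97 for an active arm with 33% stopping. These sizes are illustrations; the structural point does not depend on them. The change is worth making because it uses data already collected and concerns the safety question that arises when NUC is withdrawn.

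**What to change.** In SAP 4.5.3, split the paragraph by event.

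- **Relapse, by arm.** Keep n/N over the safety population, labelled as regimen burden. Add the number who stopped NUC, relapses among them (n/N at risk with an exact confidence interval), time from NUC stop to relapse (censored at NUC restart or end of follow-up), and the number who restarted NUC.
- **Derivation.** Flag relapse from quantitative HBV DNA above 2,000 IU/mL after the recorded NUC stop date, including unscheduled and local results. State whether the first or the confirmed value counts. Reconcile the flag with CRF-reported events in a listing.
- **Breakthrough.** Report it separately over participants on treatment. This clarifies presentation and does not correct an error.
- **No between-arm test of relapse.** Control may have about one stopper (30 × 0.03 = 0.9).

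The cost is a short SAP edit and some extra programming, because the flag needs NUC stop and restart dates as well as laboratory data. No new data collection and no change to any clinical rule is involved. With few stoppers the intervals will be wide, and the table should be read with that in mind.

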4.5.3.1 Laboratory Data

All laboratory data will be reported in terms of standard ranges in System international (SI) units and will be converted from the original units as necessary.

Summary tables will detail the transformed values and change from baseline of the laboratory parameters over time by treatment group.

Absolute values and changes from baseline over time plots will be provided.

Data processing rules-

Combination Therapies for CHB—F. Hoffmann-La Roche Ltd Statistical Analysis Plan WV41073

- Unscheduled visit: If more than one visit occurred during a single visit window, then the laboratory data closest to the scheduled visit day will be used. If the two laboratory assessments were equidistant from the scheduled visit day, then the later assessment will be used.
 - All unscheduled labs will be included in lab profile plots over time, and also listed by day relative to start of treatment including the clinical planned event CPE (visit) listed also.
- 2) Baseline visit: If the baseline value is missing, value from closest screening visit will be used. If two or more samples were collected on the day that was closest to the Baseline target day, then the earliest sample was selected; if the sample collection time was the same then the worst value was selected.
- Values below limit of quantification will be set to limit of quantification.
- 4) Local laboratory results may be available. If both local and central laboratory results are available for same time point, then central lab results should be used for analyses. In cases where only the local laboratory results exist for a given timepoint, these will be normalized using the Roche document for analysis Data Analysis Guidance: Safety Lab standardization (Please refer the output specification).

Laboratory Abnormalities:

Division of AIDS (DAIDS) Table for Grading the Severity of Adult and Pediatric Adverse Events AE grading will be used to present shifts from baseline to the worst grade observed during treatment. For protocol-required safety laboratory assessments, please refer to protocol Appendix 4- Table 1.

Shift tables will provide shifts from DAIDS grade at baseline to DAIDS grade on treatment, where baseline is defined as the last valid, non-missing assessment prior to the first study drug administration, and percentages are based on the number of participants with valid measurement at baseline.

For all laboratory parameters included in this analysis, all the laboratory values and reference ranges will be converted into standard units if it is not in a standard unit. Laboratory values falling outside this reference range will be labeled "H" for high or "L" for low in participant listings of laboratory data. If the values fall outside of reference ranges, then "H" or "L" concatenate with the DAIDS grading and will be listed.

Abnormal Live Function Tests:

Participants with ALT increased (DAIDS grade 1 or higher) will be summarized by treatment group based on Safety population.

In addition, longitudinal participates profiles for each participant will be presented:

Liver Function test profiles: Double-axis plots including ALT, AST, ALP, Direct Bilirubin, Total Bilirubin, INR.

ALT/Virology profiles: Double-axis plots displaying ALT (as ratio over ULN), HBeAg, HBsAg, HBV DNA, HBV RNA, HBcrAg (log10)

The incidence of the following LFT abnormalities will be presented by treatment arm:

- Treatment-emergent ALT/AST > 3 x ULN and >3 x BSL, in combination with total bilirubin > 2 x ULN.
- Treatment-emergent ALT or AST > 3 x ULN and >3 x BSL, in combination with clinical jaundice.

In addition, an eDISH plot (Evaluation of Drug-Induced Serious Hepatotoxicity) will be created

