All safety analyses will be based on the entire safety analysis population (Table 5). The safety data, including AEs, reasons for withdrawal from study, laboratory data, ECGs, concomitant medications, vital signs, and physical examination results will be listed and summarized descriptively. Marked abnormalities will be flagged for laboratory data. As appropriate, listings, summary tables and graphs (participant plot and/or mean plots) will be provided for safety and tolerability assessments.

 Table 5
 Safety Statistical Analysis Methods

Endpoint	Statistical Analysis Methods
Adverse events	The original terms recorded on the eCRF by the Investigator for adverse events will be coded by the Sponsor.
	Adverse events will be summarized by mapped term and appropriate thesaurus level.
Clinical laboratory tests	All clinical laboratory data will be stored on the database in the units in which they were reported. Laboratory test values will be presented in International System of Units (SI units; Système International d'Unités) by tabular summaries, individual listings with flagging of abnormal results.
	Division of AIDS (DAIDS) Table for Grading the Severity of Adult and Pediatric Adverse Events AE grading will be used to present shifts from baseline to the worst grade observed during treatment
	See Appendix 4 for details on standard reference ranges and data transformation and the definition of laboratory abnormalities.
Vital signs	Vital signs data will be presented by individual listings with flagging of values outside the normal ranges and flagging of abnormalities. In addition, tabular summaries will be used, as appropriate.
ECG data analysis	ECG data will be presented by individual listings. In addition, tabular summaries will be used, as appropriate.
Concomitant medications	The original terms recorded on the participants' eCRF by the Investigator for concomitant medications will be standardized by the Sponsor by utilizing a mapped term and appropriate drug dictionary level.
	Concomitant medications will be presented in summary tables and listings.

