Appendix 7-Table 2 Schedule of Activities for NUC Control Arm

	Scree	Screening Treatment Period											Foll	ow-up	Period					VB/VR	UV(Flu like/ ET) ^p
Week			1	4	12	24	36	48 ⁿ	2 °	4°	6 °	8 °	10 °	12	16 ⁰	20 °	24 q	36	48		-
Day	-56 to -7	-14 to -7	1	28 (± 3)	84 (± 3)	168 (± 7)	252 (± 7)	336 (± 7)	14 (±3)	28 (±3)	42 (±3)	56 (±3)	70 (±3)	84 (±7)	112 (±7)	140 (±7)	168 (±7)	252 (±7)	336 (±7)		
Informed consent	х																				
Demography, medical history	х																				
Physical examination, vital signs ^{a, b}	х		х	х	х	х	х	х									х		x	х	х
Randomization			Х																		
ECG	Х		Х		Х	Х	Х	х									Х		х		
Transient elastography/ARFI/MR ^c	х																				
Abdominal ultrasound	х					х		х									х		х		
Alfa-fetoprotein	х					х		х									х		Х		
HAV, HCV, HDV, HEV, HIV	х																				
Autoantibodies ^d	х																				
Alcohol and drugs of abuse screen ^e		х						х													х
Pregnancy test ^f		х			х	х	х	х						х			х	х	х		
Thyroid function tests	х				х	х		х									х		х		
Hematology (include HbA1c ^g)	х		х		х	х		х	х	х	х	х	х	х	х	х	х	х	х	х	х
Chemistry		х	х		х	х		х	х	х	х	х	х	х	х	х	х	х	х	x	х
Coagulation	х		Х		х	х		х	х	х	х	х	х	х	х	х	Х	х	х	x	х
GLDH	х		Х		х	х		х	х	х	х	х	х	х	х	х	х	х	х	x	х
Urinalysis	х		х		х	Х		х	х	х	х	Х	х	х	х	х	х	х	х	x	х

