intra-hepatic viral parameters including but not limited to HBsAg, HBV DNA, HBcrAg, HBV RNA, cccDNA. Where feasible, residual tissue samples may be used to measure immunological parameters (e.g., HBV specific T-cells) and/or routine histopathology. Participation in the liver biopsy sub-study will require a separate consent and will involve a select number of participants.

For further details, refer to the study operations manual.

A9.12 SCHEDULE OF ACTIVITIES siRNA + NUC ARM

An overview of the schedule of the activities is provided in Appendix 9-Table 3 and Appendix 9-Table 4.

Appendix 9-Table 3 Schedule of Activities for siRNA (100 mg or 200mg) + NUC Treatment Arm (Screening and Treatment Periods)

	Scree	ening	Treatment Period														VB/VR	ET/UV ^q
Week			1	3	5	9	13 ^{n, p}	17	21	25°,p	29	33	37	41	45	49 ^p		
Day	-56 to -7	-14 to -7	1	15 (±2)	29 (±3)	57 (±3)	85 (±3)	113 (±3)	141 (±3)	169 (±3)	197 (±3)	225 (±3)	253 (±3)	281 (±3)	309 (±3)	337 (±3)		
Informed consent	Х																	
Demography, medical history	х																	
Physical examination, vital signs ^{a, b}	Х		х	х	Х	Х	х	Х	х	Х	х	Х	Х	Х	Х	Х	х	х
Randomization			Х															
ECG	Х		Х	Х	х	Х	х	Х	х	х	х	Х	Х	х	Х	Х		
Transient elastography/ARFI/MR °	Х																	
Abdominal ultrasound	Х									Х						Х		
Alfa-fetoprotein	х									х						х		
HAV, HCV, HDV, HEV, HIV	х																	
Autoantibodies d	х																	
Alcohol and drugs of abuse screen e		Х														Х		х
Pregnancy test f		Х	Х		Х	Х	Х	Х	х	Х	Х	Х	Х	Х	Х	Х		х
Thyroid function tests	Х						х			х			Х			Х		
Hematology (includes HbA1c ⁹)	х		х	х	х	х	х	х	х	х	х	Х	х	х	х	Х	х	х
Chemistry		Х	Х	Х	Х	Х	Х	Х	х	Х	х	Х	Х	Х	Х	Х	х	х
Coagulation	Х		Х	Х	Х	Х	Х	Х	х	Х	х	Х	Х	Х	Х	Х	х	х
GLDH	Х		Х	Х	Х	Х	Х	Х	х	Х	Х	Х	Х	Х	Х	Х	х	х
Urinalysis	х		х	х	х	х	х	х	х	х	х	х	х	х	х	х	х	х
Clinical genotyping ^h			х															
HBV serology (HBsAg, HBeAg, anti-HBs, anti-HBe)	х		х	х	х	х	х	х	х	х	х	х	х	х	х	х	х	х

Appendix 9-Table 3 Schedule of Activities for siRNA (100 mg or 200 mg) + NUC Treatment Arm (Screening and Treatment Periods) (cont.)

	Scree	ening							Treatm	nent Pe	riod						VB/VR	ET/UV ^q
Week			1	3	5	9	13 ^{n, p}	17	21	25 ^{o,p}	29	33	37	41	45	49 ^p		•
Day	-56 to -7	-14 to -7	1	15 (±2)	29 (±3)	57 (±3)	85 (±3)	113 (±3)	141 (±3)	169 (±3)	197 (±3)	225 (±3)	253 (±3)	281 (±3)	309 (±3)	337 (±3)		
HBV DNA quantitative	Х		Х	Х	Х	Х	Х	Х	Х	Х	Х	Х	Х	Х	Х	Х	х	Х
Total HBsAg ⁱ			Х		Х		х			х			Х			Х	х	
HBcrAg			х		х		х			х			х			Х	х	

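### By-arm worst-grade laboratory shifts set 3 scheduled on-treatment samples in control against 13 to 18 in the siRNA arms, so experimental arms tend to look worse even at equal risk

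*SAP*

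**What the plan says.** SAP 4.5.3.1 states that DAIDS grading "will be used to present shifts from baseline to the worst grade observed during treatment". Table 5 of the protocol (section 9.4.3) plans the same display: "AE grading will be used to present shifts from baseline to the worst grade observed during treatment". The SAP sets the denominator as follows: "percentages are based on the number of participants with valid measurement at baseline". The number of later samples therefore plays no part. SAP 4.5 adds that "All safety analyses will be based on the safety analysis population grouped according to the treatment assigned at randomization".

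SAP 4.5.3.1 also summarizes, by treatment group, the participants whose ALT rose to DAIDS grade 1 or higher. It does not say which values count. Separately, it plans tables and plots of values and changes from baseline over time by group, graded listings, individual liver-test profiles and an eDISH plot.

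The sampling times are in the arm appendices of the protocol. In "Appendix 7-Table 2 Schedule of Activities for NUC Control Arm" the safety panels are marked on treatment at Weeks 12, 24 and 48, and are blank at Weeks 4 and 36. The siRNA arms are sampled about every 4 weeks, with denser sampling around TLR7 cycle starts and weekly sampling during PD-L1 LNA dosing. Neither document mentions this difference when it describes the shift table.

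**The concern.** The worst grade is a maximum. Taken over 13 or more samples it will usually be higher than when taken over 3, whether or not the drug does anything. A by-arm table of this maximum mixes two things: drug effect and number of looks.

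This matters because section 3 of the protocol says the study will compare safety as well as efficacy with control. Laboratory abnormalities are also among the interim safety endpoints in SAP 4.7.1, and the Internal Monitoring Committee reviews the interim results. Appendix 7 treats a positive benefit/risk profile as a condition for starting an expansion cohort. The error can run either way: a harmless regimen may look toxic, or a real signal may be put down to extra sampling.

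**Working it through.** The plan states no figure of its own on this point, so there is none to reproduce.

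**Step 1: count scheduled visits.** These are post-baseline, on-treatment visits at which hematology, chemistry, coagulation, GLDH and urinalysis are all marked. Day 1 is baseline.

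| Arm | Source in protocol | Visits | Count |
|---|---|---|---|
| NUC control | Appendix 7-Table 2 | Weeks 12, 24, 48 | 3 |
| siRNA + NUC (100 or 200 mg) | Appendix 9-Table 3 | Weeks 3, 5, 9, 13, 17, 21, 25, 29, 33, 37, 41, 45, 49 | 13 |
| siRNA + PEG-IFN + NUC | Appendix 10-Table 3 | same weeks | 13 |
| siRNA + TLR7 + NUC | Appendix 12-Table 4 | same weeks, plus 2 extra visits at each of 2 cycle starts | 17 |
| siRNA + PD-L1 LNA, 24 weeks | Appendix 13-Table 7 | Days 29, 57, 85, then weekly to Day 169 | 15 |
| siRNA + PD-L1 LNA, 36 weeks | Appendix 13-Table 8 | Days 29, 57, 85, 113, 141, then weekly Days 169 to 253 | 18 |

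The terminated siRNA + CpAM arm (Appendix 11-Table 3) also has 13. Thyroid tests are nearly balanced: 3 in control and 4 in siRNA + NUC.

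**Step 2: chance of at least one graded value when the true risk is equal.** Let *p* be the chance of a graded value at one visit, *k* the number of visits and ρ the within-participant correlation. Neither *p* nor ρ is in the documents; both are assumed over a range.

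- Independent visits: P = 1 − (1 − *p*)^*k*. For *p* = 2%: 1 − 0.98^3 = 5.9% and 1 − 0.98^13 = 23.1%.
- Correlated visits (beta-binomial): with *a* = *p*(1 − ρ)/ρ and *b* = (1 − *p*)(1 − ρ)/ρ, P = 1 − B(*a*, *b* + *k*)/B(*a*, *b*). For *p* = 2%, ρ = 0.5 and *k* = 3, *a* = 0.02 and *b* = 0.98, so P = 1 − 0.98 × (1.98/2) × (2.98/3) = 3.6%.

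Each cell gives 3 visits against 13:

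| ρ | *p* = 1% | *p* = 2% | *p* = 5% | *p* = 10% |
|---|---|---|---|---|
| 0 | 3.0% / 12.2% | 5.9% / 23.1% | 14.3% / 48.7% | 27.1% / 74.6% |
| 0.1 | 2.7% / 8.0% | 5.3% / 15.5% | 13.0% / 34.6% | 24.8% / 57.9% |
| 0.3 | 2.2% / 4.7% | 4.4% / 9.3% | 10.8% / 21.8% | 20.8% / 39.3% |
| 0.5 | 1.8% / 3.1% | 3.6% / 6.2% | 8.9% / 14.9% | 17.4% / 27.8% |
| 1 | 1.0% / 1.0% | 2.0% / 2.0% | 5.0% / 5.0% | 10.0% / 10.0% |

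At *p* = 2% and 30 participants per arm, the expected counts are 1.8 against 6.9 (ρ = 0), 1.3 against 2.8 (ρ = 0.3) and 1.1 against 1.9 (ρ = 0.5). With 18 visits and ρ = 0 the arm percentage is 30.5%.

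**Step 3: what matching on visits does.** Control Days 84, 168 and 336 correspond to Days 85, 169 and 337 in the 48-week siRNA arms, so each arm contributes 3 visits. Equal risk then gives equal percentages (5.9% each at *p* = 2%, ρ = 0). The 24-week PD-L1 LNA arm shares 2 visits with control (4.0% each). The 36-week arm shares the same two, but its LNA is given in Weeks 25 to 36. Protocol section 8.11.2 puts assessments before dosing, so the Day 169 sample is taken before the first LNA dose. Control has no safety panel at Week 36.

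**The case against.** Four points can be made for the plan.

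- **Other displays are planned.** Values and changes over time by treatment group can be compared at shared visits with no number-of-looks problem. This stands. A reader might infer that the SAP leaves no unaffected laboratory comparison between arms, and that is wrong. What is not stated is a matched-visit comparison of *grades*. Table shells sit in output documents that are not public, so such a display cannot be excluded.
- **The size may be modest.** Repeat values in one person are usually correlated. A reader might infer from 5.9% against 23.1% that the siRNA arms will look about four times worse. That figure needs independent visits and an assumed rate, and the documents support neither. This stands.
- **The study is exploratory.** No hypothesis is tested, no documented rule uses the shift table as a threshold, and the lean is toward flagging a signal. This limits the consequence. It does not make a by-arm table unbiased.
- **Matching can mislead in the other direction.** In the TLR7 arm the Day 85 sample comes before the first TLR7 dose, and the extra cycle-start visits would be dropped. Yet A12.11 says hematological abnormalities mostly reversed within 24 to 48 hours. A13.3 reports frequent transient low-grade ALT elevations at the highest LNA regimen in Phase 1. A matched table alone could make these arms look safer than they are. This stands, and it limits how the table may be used.

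**Conclusion.** The concern holds for hematology, chemistry, coagulation, GLDH and urinalysis. With 3 scheduled visits in control and 13 to 18 in the siRNA-containing arms, the by-arm worst-grade shift table tends to make experimental arms look worse at equal risk. The ALT grade 1 or higher summary shares the weakness if it counts any on-treatment value. The direction follows from taking a maximum and fails only if abnormalities persist perfectly.

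The size cannot be determined from the documents. Over the assumed rates and correlations, the 13-visit to 3-visit ratio runs from about 4.1 (independent visits, *p* = 1%) down to 1.0 (ρ = 1). At *p* = 2% it is about 2.1 at ρ = 0.3 and 1.7 at ρ = 0.5. All counts are as scheduled; the pandemic-related missed visits and any unscheduled tests will change them.

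Two wider readings are not supported. The point does not cover all laboratory tests, since thyroid sampling is close to balanced. Nor does it show that an excess seen in an experimental arm would be artefact; it shows only that this table cannot tell.

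**What to change.** In SAP 4.5.3.1:

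1. Keep the full worst-grade shift table as the main safety display, and show the number of on-treatment assessments per participant by arm beside it.
2. State which values count in the ALT grade 1 or higher summary.
3. Add a supportive worst-grade shift table for each experimental arm against control, restricted to the on-treatment visits that the pair shares: Weeks 12/13, 24/25 and 48/49 for the 48-week arms, and Weeks 12/13 and 24/25 for the 24-week PD-L1 LNA arm.
4. For the 36-week PD-L1 LNA arm, give the assessment counts and a caveat, not a matched comparison of LNA effect.
5. State the limitation with the table: it leaves out visits timed to catch transient effects, such as TLR7 cycle starts, so it must not replace the full table or be read as evidence of safety.

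The cost is a small set of pairwise tables and one row of counts from data already collected. No sample or visit is added. SAP 5.3 and 5.4 already foresee a later version of the plan that could carry the change. The price in information is that the matched tables use few visits and will be imprecise with about 30 participants per arm.
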